11.2. Study duration

12 weeks with 4 visits to the study site (W0, W4 ± 3 days, W8 ± 3 days and W12 ± 3 days) per subject.

An interval of at least 1 month must be respected before the subject will be allowed to participate in another study.

11.3. Study restrictions

Throughout the study, subjects will be instructed as follows:

- to replace their usual skin care products for the face with the IP according to the instructions and not to apply any other topical products
- to continue to use their usual non-comedogenic washing products and shampoo (no new product)
- to continue to use their usual make-up and remover (no new product)
- not to expose to excessive sunlight
- not to expose to artificial UV light
- not to undergo surgical/medical procedures on the face (deep cleansing, dermabrasion, peeling, light-therapy, laser...)
- not to use scrub, not to apply self-tanning product on the face
- not to manipulate the imperfections on the face (do not scratch, squeeze...)
- not to change as far as possible their routine lifestyle (food...)
- not to apply any topical products (including IP, make-up...) on face the day of the visits
- not to wash the face and/or the hair the day of the visits (only water is accepted the morning of the visits)
- to return the daily log and the IP at each visit
- to store the IP (cosmetic product) at ambient temperature and the IP (drug treatment) at a temperature not exceeding 25°C at home

Subjects will be informed of the restrictions verbally and in writing prior to consenting to take part in the study.

11.4. Prior and concomitant medication

Any topical or systemic therapy used in the 4 weeks prior the Visit 1 will be recorded in the CRF, with the following information:

- name of the drug, type of formulation, and unit strength,
- dose administered,
- start and stop dates,
- reason for treatment.

The following treatments are not allowed:

- isotretinoin treatment within the 6 months prior the Visit 1 and during the study
- surgical/medical procedures on the face (deep cleansing, dermabrasion, peeling, light-therapy, laser...) during the study,
- systemic drugs for more than 3 consecutive days related to antibiotics, anti-inflammatory, corticoids, anti-acneic in the 4 weeks prior the Visit 1 and during the study,
- topical drugs for more than 3 consecutive days related to antibiotics, anti-inflammatory, corticoids, anti-acneic in the 2 weeks prior the Visit 1 and during the study,

Any subject using a concomitant therapy during the study that could interfere with the assessment of the IP will be considered for withdrawal from the study, at the discretion of the investigator.

11.5. Study schedule

Having received all the written and verbal information and the answers to them questions, the subjects and all legal representatives (for minor subjects) must give their consent by signing the Consent Form.

For females of childbearing potential (except those who are surgically sterile): a urinary pregnancy test will take place on W0, before IP dispensation.

Investigators will provide the pregnancy test kit funded by the Sponsor.

Then the following examinations are made:

• VISIT 1 - W0

- Inform Consent
- Demographics
- Medical history ⁽¹⁾ / previous and concomitant medications ⁽²⁾
- Checking of inclusion and exclusion criteria
- Urinary pregnancy test for females of child-bearing potential
- Counting of the retensional (open & closed comedones) and inflammatory lesions (papulae, pustulae & nodules (if applicable)) on the face by the Dermatologist
- Determination of the acne stage according to the GEA scale by the Dermatologist
- Definitive inclusion
- Clinical assessments by the Dermatologist (skin quality efficacy and local tolerance)
- Microbiota sampling by a technician and/or a nurse
- Instrumental measurements by a technician and/or a nurse (different according to the study centre) & confocal microscopy by investigator (Nantes site only)
- Dispense IP according the randomisation and daily log
- Explanation of usage instructions

⁽¹⁾ Details of relevant medical or surgical history experienced over the subject's life time, including any allergies or sensitivities, may include physical examination.

⁽²⁾ Details any medication taken in the 4 weeks prior the Visit 1.

• **VISIT 2 – W4 (±3 days) (AFTER A 4-WEEK APPLICATION PERIOD)**

- Confirm health status of subject and record any concomitant therapies and adverse events
- Return of IP and daily log
- Check of subject completed daily log for compliance with products usage
- Dispense IP according the randomisation and daily log
- Counting of the retentional (open & closed comedones) and inflammatory lesions (papulae, pustulae & nodules (if applicable)) on the face by the Dermatologist
- Determination of the acne stage according to the GEA scale by the Dermatologist
- Clinical assessments by the Dermatologist (skin quality efficacy and local tolerance)
- Instrumental measurements by a technician and/or a nurse (different according to the study centre)
- Explanation of usage instructions

• **VISIT 3 – W8 (±3 days) (AFTER A 8-WEEK APPLICATION PERIOD)**

- Confirm health status of subject and record any concomitant therapies and adverse events
- Return of IP and daily log
- Check of subject completed daily log for compliance with products usage
- Dispense IP according the randomisation and daily log
- Counting of the retentional (open & closed comedones) and inflammatory lesions (papulae, pustulae & nodules (if applicable)) on the face by the Dermatologist
- Determination of the acne stage according to the GEA scale by the Dermatologist
- Clinical assessments by the Dermatologist (skin quality efficacy and local tolerance)
- Instrumental measurements by a technician and/or a nurse (different according to the study centre)
- Explanation of usage instructions

• **VISIT 4 – W12 (±3 days) (AFTER A 12-WEEK APPLICATION PERIOD)**

- Confirm health status of subject and record any concomitant therapies and adverse events
- Return of IP and daily log
- Check of subject completed daily log for compliance with products usage
- Completion of the cosmetic acceptability and efficacy questionnaires by the subject
- Counting of the retentional (open & closed comedones) and inflammatory lesions (papulae, pustulae & nodules (if applicable)) on the face by the Dermatologist
- Determination of the acne stage according to the GEA scale by the Dermatologist
- Clinical assessments by the Dermatologist (skin quality efficacy and local tolerance)
- Products overall tolerance appreciation by the Dermatologist and the subject
- Microbiota sampling by a technician and/or a nurse
- Instrumental measurements by a technician and/or a nurse (different according to the study centre) & confocal microscopy by investigator (Nantes site only)

[figure not shown]
11.6. Study assessments

For 1 subject, clinical assessments should be performed by the same investigator for the whole study except in case of absolute necessity.

11.6.1. Primary variable: Counting of the retentional and inflammatory lesions (anti-acne efficacy)

At W0 (before any application) and W12 (after a 12-week application period), a counting of the retentional (open & closed comedones) and inflammatory lesions (papulae, pustulae & nodules (if applicable)) will be performed by a Dermatologist.

The counting will be broken down on several parts of the face according to the following pictures: forehead, left and right cheeks and chin.

The number and sum of open & closed comedones (retentional lesions) and of papulae, pustulae & nodules (if applicable) (inflammatory lesions) will be recorded in the CRF.

[figure not shown]
11.6.2. Secondary variables

11.6.2.1. Anti-acne efficacy

- Counting of the retentional and inflammatory lesions

At W4 (after a 4-week application period) and W8 (after an 8-week application period), a counting of the retentional (open & closed comedones) and inflammatory lesions (papulae, pustulae & nodules (if applicable)) will be performed by a Dermatologist.

The counting will be broken down on several parts of the face according to the following pictures: forehead, left and right cheeks and chin.

The number and sum of open & closed comedones (retentional lesions) and of papulae, pustulae & nodules (if applicable) (inflammatory lesions) will be recorded in the CRF.

- Determination of the acne stage

At W0 (before any application), W4 (after a 4-week application period), W8 (after an 8-week application period) and W12 (after a 12-week application period), determination of the acne stage will be performed by the Dermatologist according to the Global Acne Evaluation scale (cf Appendix 2) and will be recorded in the CRF.

11.6.2.2. Skin quality efficacy

- Clinical assessments

At W0 (before any application), W4 (after a 4-week application period), W8 (after an 8-week application period) and W12 (after a 12-week application period), clinical assessments will be performed under the same conditions by the Dermatologist:

- of the residual marks visibility of acne (hyperpigmentation)
- of the pores visibility
- of the skin shininess

using the scales below which include 10 grades (0 to 9).

| Residual marks visibility of acne (hyperpigmentation) | | | | | | | | | |
|---|----------------------------|---|---|--------------------------------|---|---|---------------------------------|---|---|
| 0 | 1 | 2 | 3 | 4 | 5 | 6 | 7 | 8 | 9 |
| Absence of visible residual marks | Few visible residual marks | | | Several visible residual marks | | | Numerous visible residual marks | | |

| Pores visibility | | | | | | | | | |
|--------------------------|-------------------|---|---|-----------------------|---|---|------------------------|---|---|
| 0 | 1 | 2 | 3 | 4 | 5 | 6 | 7 | 8 | 9 |
| Absence of visible pores | Few visible pores | | | Several visible pores | | | Numerous visible pores | | |

| Skin shininess | | | | | | | | | |
|---------------------------|-----------------------|---|---|-------------------------|---|---|---------------------|---|---|
| 0 | 1 | 2 | 3 | 4 | 5 | 6 | 7 | 8 | 9 |
| Absence of skin shininess | Slight skin shininess | | | Moderate skin shininess | | | High skin shininess | | |

All the scores will be recorded in the CRF.

- Instrumental measurements

At W0 (before any application), W4 (after a 4-week application period), W8 (after an 8-week application period) and W12 (after a 12-week application period), instrumental measurements will be performed by a technician at Intertek and a nurse at CHU Nantes.

The subjects will rest in a climatized temperate room for at least 30 minutes before instrumental measurements.

- Skin greasiness using sebumetry measurements*

The CL measurements (quantity of sebum (casual level)) will be taken using a SEBUMETER® (COURAGE + KHAZAKA).

The measurement is based on grease-spot photometry. A special tape becomes transparent in contact with the sebum on the skin surface. For the determination of the sebum, the measuring head of the cassette is inserted into the aperture of the device, where the transparency is measured by a light source sending light through the tape which is reflected by a little mirror behind the tape. A photocell measures the transparency. The light transmission represents the sebum content on the surface of the measuring area. A microprocessor calculates the result, which is shown on the display in $\mu\text{g sebum}/\text{cm}^2$ of the skin.

Only one measurement per subject will be taken in the middle of the forehead (if it will be possible on a nonlesional skin). The value will be reported in the CRF.

- Skin moisturizing using corneometry measurements*

The measurements will be taken using a CM 825 PC CORNEOMETER® (COURAGE + KHAZAKA).

The skin acts as a condenser with a high dielectric constant, for which the capacity depends on the amount of water contained in the epidermis (water rises ion mobility). The Corneometer measures the dielectric capacity of the epidermis using a condenser.

The hydration values are expressed in arbitrary units ranging from approximately 0 to 120.

Three measurements per subject will be taken on the right cheekbone (if it will be possible on a nonlesional skin). The values will be reported in the CRF.

[figure not shown]
- Skin pH using pHmetry measurements*

The measurements will be taken using a SKIN PH METER 900® (COURAGE + KHAZAKA).

The measurement is based on the principle of electrochemistry. PH measurement allows obtaining the acidity and alkalinity of the skin. The value is determined by the hydrogen ion concentration (protons H+) and by the hydroxide ion concentration (OH- anions) and will be expressed in pH units.

The pH measurement is preferably carried out with a glass electrode. The interior of the electrode is filled with a buffer (mercury / calomel or silver / silver chloride). This buffer is separated from the measurement solution by a thin glass membrane. In contact with the solution, the buffer transports the ionic potential of the solution on the interior side toward the outer side of the glass membrane. A flat disc in front of the membrane allows direct contact on surface of the skin.

Only one measurement per subject will be taken on the left cheek, near to the side of the nose (if it will be possible on a nonlesional skin). The value will be reported in the CRF.

Sebumetry measurement

Corneometry measurements

Phmetry measurement

- *Confocal microscopy analysis (only for CHU Nantes; n≈ 30) (5)*

From the beginning of the inclusions and until the number of subjects will be reached (n≈ 30), the investigator will propose a complementary examination that the subjects will be free to refuse.

At W0 (before any application) and W12 (after a 12-week application period), instrumental measurements will be performed by investigator at CHU Nantes.

a) Acquisitions:

RCM Vivascope® (1500/3000) is a confocal laser scanning microscope for *in vivo* use, with an imaging wavelength of 830 nm, used to acquire standardized pictures of the skin. Confocal images are obtained by analyzing the reflection of a diode laser in the skin. Resolution allows analyzing the epidermis and upper layers of the stratum reticulare, up to a depth of 200 µm with a lateral resolution <1.25 µm. The lens will be directly applied onto the selected skin area (on 3 nonlesional skin area: forehead, right temple and right mandibular). Crodamol oil will be used as a conductive interface between the skin and the lens. Each image corresponded to a 500 µm x 500 µm horizontal section. A Vivacube® of 3 mm x 3 mm is a mosaic of 36 images, on three horizontal section levels.

b) Analysis:

Confocal images will be analyzed by two confocal microscopy experts ([name], [name]).

The assessments features will be:

- Total number of hair follicles per cube at a mean depth of 38 µm
- Diameter of the infundibulum
- Aspect of the border (thickness)
- Onion-like appearance
- Presence of amorphous material into the infundibulum
- Signs of inflammation
- Vascularization
- Presence of *Demodex* mites

- Efficacy questionnaire

Subjects will complete an efficacy questionnaire at the last visit (after a 12-week application period of the IP (cosmetic product & drug)).

The following items will be evaluated by the subjects:

| | ITEMS |
|----|---|
| 1 | Les imperfections sont moins visibles Imperfections are less visible |
| 2 | La peau est assainie/purifiée The skin is cleansed/purified |
| 3 | Le teint est homogène/uniforme The complexion is homogeneous / uniform |
| 4 | La peau est confortable The skin is comfortable |
| 5 | La peau est comme hydratée The skin is like hydrated |
| 6 | La peau est plus lisse The skin is smoother |
| 7 | La peau est plus douce The skin is softer |
| 8 | La peau est plus souple The skin is suppler |
| 9 | La peau est moins brillante The skin is less brilliant |
| 10 | La peau est matifiée The skin is matified |
| 11 | L'excès de sébum est réduit Excess sebum is reduced |
| 12 | La peau a un toucher mat The skin has a matte touch |
| 13 | Les pores de la peau sont resserrés The pores of the skin are tightened |
| 14 | Les rougeurs de la peau sont atténuées Redness of the skin are reduced |
| 15 | Le grain de peau est affiné The skin texture is refined |
| 16 | Les marques de la peau sont moins visibles The marks of the skin are less visible |

The following scale will be used:

- Agree (“D'accord”)
- Somewhat agree (“Plutôt d'accord”)
- Neither agree, nor disagree (“Ni d'accord ni pas d'accord”)
- Somewhat disagree (“Plutôt pas d'accord”)
- Disagree (“Pas d'accord”)

11.6.2.3. Local tolerance

- Clinical assessments

At W0 (before any application), W4 (after a 4-week application period), W8 (after an 8-week application period) and W12 (after a 12-week application period), a clinical assessment of the face skin condition will be performed by the Dermatologist:

- Physical signs: erythema, dryness and scaling
- Functional signs*: tightness, prickling, itching, burning sensation and others

The following scale will be used:

Rating 0: none ("absence")

Rating 1: slight ("léger")

Rating 2: moderate ("modéré")

Rating 3: severe ("sévère")

* During the study, the subjects will have to record any skin discomfort, intensity (slight, moderate or severe) and duration in their daily log. Functional signs will be assessed by the Dermatologist from a review of the daily log and interrogatory of the subject.

- Overall tolerance

In addition, at W12 (after a 12-week application period), the Dermatologist and the subject will state about the overall tolerance of the IP (cosmetic product & drug) based on rating scale:

- Excellent tolerance
- Good tolerance
- Medium tolerance
- Poor tolerance

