| Return of IP and daily log | | X | X | X |
| Compliance, Health and Concomitant medication checks | X | X | X | X |
| Cosmetic acceptability and efficacy questionnaires | | | | X |
| Products overall tolerance appreciation by the Dermatologist and the subject | | | | X |
| Adverse Events | X | X | X | X |
| Complete CRF, final page 'End of study' ⁽⁶⁾ | | | | X |

⁽¹⁾ Visit flexibility = ± 3 days

⁽²⁾ Details of relevant medical or surgical history experienced over the subject's life time, including any allergies or sensitivities, may include physical examination.

⁽³⁾ Details any medication taken in the 4 weeks prior to Visit 1.

⁽⁴⁾ IP application made at home until the day before the visits.

⁽⁵⁾ Completed after each IP application.

⁽⁶⁾ At Final Visit, if subject completes study as planned, or at any time before that in case of withdrawal.

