9.6. Screen failures, subject withdrawals and replacement criteria

Non-included subjects, that is, subjects who have signed informed consent but are removed from the study during the screening process because they do not meet the inclusion/exclusion criteria, are classed as screen failures. Subjects who leave the study after randomisation or assignment to study treatment are classed as withdrawals rather than screen failures, even if the subject had not started the study treatment.

Subjects not completing the study for any reason will be considered as withdrawals and will not be replaced.

Criteria for withdrawal:

1. Subject withdraws consent: subjects will be free to withdraw from the study at any time and for any reason. (In accordance with the Declaration of Helsinki),
2. Adverse event / Serious adverse event: any adverse event that the investigator considers it is not in the subject's best interest to continue,
3. Protocol deviation (after agreement of the Sponsor and/or the investigator),
4. Subject lost to follow-up,
5. Other reasons: other reasons than stated above which requires subject to be withdrawn as:
 - any other situation where, in the opinion of the investigator, continuation of the study would not be in the interest of the subject;
 - Discontinuation of the study by the Sponsor.

The CRF should be completed up to the time of screen failure or withdrawal.

A subject will be considered as "Lost to Follow-up" after 3 phone calls (recorded) and a mail (registered mail with Acknowledgement of receipt) stayed without answer.

All subjects who are prematurely discontinued from the study should have the reason carefully documented by the Investigator/study team in the CRF, final page 'End of study', and, as applicable, on the Adverse Event Form and/or Concomitant Treatment Form.

No follow-up will be planned for the withdrawn subjects.

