14.1. Sample size calculation

The primary objective of this study is to demonstrate the superiority of fla 688977 33 versus Hydréane légère on the total number of lesions at W12.

The following hypotheses, based on previous studies (4) were used for the estimation of the sample size calculation:

- Power $(1 - \beta) = 80\%$
- Two-sided significance level $(\alpha) = 5\%$
- Expected inter-treatment difference (on the changes W12-W0) = 1.15
- Standard deviation = 5.0
- Correlation between the baseline and the endpoint $R^2 = 0.70$

Using the sample size calculation method for covariance analysis (7), the number of evaluable subjects is estimated at 90 by treatment group (180 subjects total).

If we anticipated 10% of drop-out, the total number of subjects required is 200.

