Physical and functional signs will be described and analysed using a generalized linear random model for multinomial data (a model for binary data can also be used according to the results of the descriptive analysis), with Subject as random factor, Time and Product as fixed factors (SAS® Glimmix Procedure).

The overall tolerance will be compared between treatments using a chi-square test.

The adverse events will be described and the number of subjects with at least one AE related to the study product will be compared between products by a chi-square test.

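### Subjects who leave before W12 because of a skin reaction have no overall tolerance rating and are absent from its chi-square test; the reaction itself may also go unrated in the signs analysis

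*Combined protocol and SAP*

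**What the plan says.** Section 7.2 makes better local tolerance a secondary objective and words it as something to demonstrate. Section 11.6.2.3 gives it two measures.

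- **Signs.** Physical and functional signs are graded 0 to 3 at W0, W4, W8 and W12. Functional signs are graded by the dermatologist from the daily log and by questioning the subject.
- **Overall tolerance.** This has four levels, from excellent to poor: "In addition, at W12 (after a 12-week application period), the Dermatologist and the subject will state about the overall tolerance of the IP". The flow chart in section 4 marks it in the W12 column only.

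Section 9.6 lists an adverse event as a ground for withdrawal, does not replace withdrawn subjects and plans no follow-up of them. On records it says: "The CRF should be completed up to the time of screen failure or withdrawal". The only flow-chart item tied to early exit is the end-of-study page, through footnote 6: "At Final Visit, if subject completes study as planned, or at any time before that in case of withdrawal".

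Section 14.2 analyses safety on all randomised subjects with at least one application of each product. Section 14.3 models the signs longitudinally with a random subject effect. For the other measure it says: "The overall tolerance will be compared between treatments using a chi-square test". It gives no rule for a missing rating.

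**The concern.** Whether an overall rating exists depends on the outcome being rated. A subject who stops because of burning or erythema has a poor tolerance outcome and, for that reason, supplies no rating. Membership of the ITT set does not help, because it adds the subject to the population without adding a value.

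The test then compares only those who reached W12. If the study product prevents withdrawals for skin reactions, the test does not credit that benefit. If it causes more of them, the test does not count that cost. Either way, the result is a weak basis for an objective framed as a demonstration.

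**Working it through.** **1. The plan's own figure.** Section 14.1 sizes the trial on the lesion count: difference 1.15, SD 5.0, R² = 0.70, two-sided 5%, power 80%.

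n per arm = 2 × (1.960 + 0.842)² × (5.0/1.15)² × (1 − 0.70) = 296.74 × 0.30 = 89.02, rounded up to 90. Then 180/0.90 = 200.

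The figure reproduces but says nothing about tolerance. What it supplies here is the planned drop-out: 10% of 200 = 20 subjects, with no split by arm or reason.

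**2. What each early leaver contributes under the plan.**

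| Exit | Scheduled sign ratings kept | Overall rating |
|---|---|---|
| Before W4 | W0 only | none |
| W4 to before W8 | W0, W4 | none |
| W8 to before W12 | W0, W4, W8 | none |
| Completes | all four | yes |

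The gap in overall tolerance covers every early leaver. In the signs analysis, only exit before W4 leaves no post-baseline score. For any early leaver, a reaction that arises after the last visit may go unrated. The model must then treat it as missing at random, which is doubtful when that reaction caused the exit.

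**3. Fixed-count illustration (upper bound).** Assumptions: 100 per arm, all 20 planned drop-outs are skin-reaction withdrawals, and 10 completers per arm are rated medium or poor. Pearson chi-square without continuity correction, comparator v study product:

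| Withdrawn | Completers only | Withdrawals counted as medium/poor |
|---|---|---|
| 10 / 10 | 10/90 v 10/90 = 11.1% v 11.1%, p = 1.00 | 20% v 20%, p = 1.00 |
| 15 / 5 | 10/85 v 10/95 = 11.8% v 10.5%, p = 0.79 | 25% v 15%, p = 0.077 |
| 18 / 2 | 10/82 v 10/98 = 12.2% v 10.2%, p = 0.67 | 28% v 12%, p = 0.005 |

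Reversed splits give the mirror image. An equal split leaves the difference undistorted.

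**4. Simulation on assumed rates.** 100 per arm; withdrawal for a local reaction as shown, plus 4% for other reasons in each arm; completers in both arms rated excellent/good/medium/poor at 40/40/15/5%. Withdrawals for other reasons are left out of both analyses.

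Expected share rated poor when local-reaction withdrawals count as poor, at 8% v 2%: (0.05 × 88 + 8)/96 = 12.9% v (0.05 × 94 + 2)/96 = 7.0%.

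| Local-reaction withdrawal | Rejects as written | Rejects, counted as poor |
|---|---|---|
| 10% v 2% | 5% | 27% |
| 8% v 2% | 5% | 18% |
| 6% v 4% | 5% | 6% |
| 5% v 5% | 5% | 5% |

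The 8% v 2% figure of 18% varies between 17% and 18% over repeated runs. The 5% as written holds by construction, because completers in the two arms are given the same distribution.

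**5. The existing backstop.** Section 14.3 also compares the number of subjects with at least one related AE. Assume each local-reaction withdrawal is recorded as a related AE and other related AEs occur at an equal background rate in both arms.

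| Background rate | AE test rejects, 8% v 2% | AE test rejects, 10% v 2% |
|---|---|---|
| 0% | 49% | 69% |
| 5% | 28% | 42% |
| 10% | 19% | 29% |
| 20% | 12% | 18% |

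**The case against.** Three stronger readings are tempting, and the documents support none of them.

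- **Subjects who withdraw for a reaction vanish from the tolerance analysis altogether.** This is not so for the signs. The longitudinal model in section 14.3 uses every rating made before exit, and the daily log (section 11.6.2.3) records the intensity and duration of discomfort between visits.
- **The plan hides an irritant product.** It does not. Related AEs are compared between products on all exposed subjects (sections 14.2 and 14.3). Each AE record carries causality, severity and action taken, and related AEs still present at the end of participation are followed up (section 11.7.1.2). Withdrawals are tabulated by product group and by reason (section 14.3). In step 5 the AE test finds the 8% v 2% imbalance at least as often as the re-scored tolerance test until the background rate exceeds about 10%.
- **The comparison is necessarily pulled towards no difference.** That requires unequal withdrawal for reactions. The documents give no split, and at 6% v 4% the effect is negligible.

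A fair further objection is that scoring every such withdrawal as poor overrides both raters, since a mild reaction can also prompt a subject to leave. That argues for a rating at exit, with the scoring rule kept as a sensitivity analysis.

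These points narrow the concern but do not remove it. The AE test counts one slight related event the same as a reaction that ends participation. The withdrawal table carries no planned comparison. Neither is the local tolerance variable. The separate SAP due before database lock (section 14) could add a missing-data rule, but it cannot supply ratings that were never collected.

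**Conclusion.** The concern holds in limited form. Followed exactly, the plan gives no overall tolerance rating to anyone who leaves before W12, so the chi-square on that variable omits those whose tolerance was bad enough to end participation. For the signs, the loss is confined to leavers before W4, who have no post-baseline score, and to unrated reactions that led to a later exit.

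The overall tolerance comparison is distorted only if these withdrawals differ between arms. Size and direction cannot be derived from the documents. On assumed rates, the change in rejection runs from nil (5% v 5%) through 5% to 6% (6% v 4%) to 5% to 18% (8% v 2%). These figures depend on the assumed withdrawal split, on identical ratings among completers and on counting withdrawals as poor.

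The point affects one secondary objective, not the primary one. It should be corrected because the gap is definite and the correction is cheap.

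**What to change.** - **Collection.** In section 11.6.2.3, the flow chart and its footnote 6, have the physical and functional signs and both overall tolerance ratings completed at W12 or at withdrawal, on the existing CRF pages.
- **Main analysis.** In section 14.3, compare overall tolerance using the last such rating in all exposed subjects, and show the completers-only table as supportive.
- **Sensitivity analysis.** Count a subject withdrawn for a local skin reaction without an exit rating as having poor tolerance.

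The cost is one short extra rating at the withdrawal contact and a few sentences of text. There are two drawbacks. Exit ratings follow unequal exposure times, and in the sensitivity analysis subjects who do not return are classified by rule from the recorded reason instead of being rated.
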